10.3.11. Week 52 Visit (for Open-Label Extension Period only)

- Measure clinic BP and pulse.
- Record AESIs/SAEs since the previous visit.
- Collect blood and urine samples.
- Review all medications being taken by the participant.
- Collect unused study medication (if applicable).
- Stop study medication and prescribe alternate BP-lowering treatment in line with local guidelines/practice.
- Ask participants to report any AESIs/SAEs during 14 days after the end of study medication
- Explain that the trial follow-up is now completed and thank participant.

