9.2.3. Descriptive Safety Outcomes

In addition, descriptive safety data will be reported on:

- Percentage of participants discontinued trial medication due to AE/SAE during the placebo run-in period.
- All AESI and SAEs, by severity and by System Organ Class (SOC) criteria during the run-in period, by trial medication group during the randomized treatment period, and safety follow-up period or Open-Label Extension Period.

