17.2. Safety Reporting

17.2.1. AESI/SAE Data Collection & Follow-Up Period

AESI/SAE data will be collected and followed-up from the time signed informed consent is obtained and up to the Week 8 EOT visit for the double-blind period. For participants continuing in the Open-Label Extension Period, AESIs/SAEs will be collected up to and including the Week 52 visit. Follow-up information on ongoing AESIs/SAEs obtained after the participant's respective EOT visit (as applies) will not be collected in the eCRF.

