17.2.3. Reporting of AESIs & SAEs

At each trial scheduled visit and unscheduled visits during the trial, site staff will ask participants about the incidence of any AESIs or SAEs since the previous visit. Other AEs will not be recorded since these drugs are well-known and established with widespread use. Site staff may also become aware of the incidence of AEs during a phone call with participants. All SAEs that site staff becomes aware of from the time informed consent is obtained until 30 days after discontinuation of the trial medication must be recorded. The following information will be collected for each AESI and SAE: event name, date of onset, severity, a possible cause of the event, relationship to trial medication, action taken regarding the trial medication, treatment given to manage the event (if applicable), the outcome of event, and date of resolution (if applicable).

An increase in the severity of a previously reported AESI or SAE during the trial will be reported as a new AESI or SAE with higher severity. A decrease in the severity of a previously reported AESI or SAE during the trial, will not require changes to the reported severity. Worsening of a condition, recurrent episodes, and further complications if any are to be reported as a follow-up of the original event.

All SAEs will be reported by the site staff to the sponsor via the eCRF within 24-hours of first becoming aware of the event. Additional information will be collected including, seriousness criteria, hospitalization date and discharge (if applicable), and procedures performed (if applicable).

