3.5.3 Study Period for Analysis

The study is planned with 3 periods ([Section 2.2.3](#)) with varying treatment assigned in both trial medication and dose level during the specified periods. For a minority of participants, FU1 may not occur at 4 weeks exactly and screening visit is not always exactly 2 weeks before Randomization visit, due to protocol-specified visit windows and administrative issues such as scheduling issues for participants. Therefore, the analysis periods will be defined:

- Period 1: From Week -2 to Randomization, defined as from screening to Randomization and Baseline Visit,
- Period 2: From Randomization to Week 4, defined as from Randomization and Baseline Visit to FU1/Week 4 visit,
- Period 3: From Week 4 to Week 8, defined as from FU1/Week 4 to EOT/Week 8,
- Post-Randomization Period: From Randomization to Week 8, defined as from Randomization and Baseline Visit to FU2 (Period 2 and Period 3).

Analysis of the optional Open-Label Extension Study will be described in a separate analysis plan.

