3.11 Analysis of Safety Endpoints

3.11.1 Adverse Events of Special Interest

3.11.1.1 Definitions & Derivations

An Adverse Event (AE) is any undesirable medical event occurring to a subject in a clinical trial, whether or not related to the trial medications.

Drug related AEs are AEs with a causality to drug being possibly, probably, definitely related or with a missing causality.

The only non-serious Adverse Events to be recorded are Adverse Events of Special Interest (AESIs). An AESI is the subset of an AEs that are due to:

- Dizziness or any other symptom or event possibly related to hypotension,
- Abnormality detected in laboratory assessments of sodium, potassium, uric acid, glucose, lipids, creatinine or eGFR,
- Symptom of pedal edema reported by the participant,
- Any other symptom or laboratory abnormality that led to treatment withdrawal.

AESI include events occurring during Run-in, Randomization Period and Follow-up.

A Serious Adverse Event (SAE) is any AE that meets one or more of the following criteria:

- Results in death;
- Is life-threatening;
- Requires in-patient hospitalization or prolongation of existing hospitalization;
- Results in persistent or significant disability/incapacity;
- Results in a congenital anomaly/birth defect.

Important medical events that may not result in death, be life-threatening, or require hospitalization may be considered serious when, based upon appropriate medical judgment, they may jeopardize the patient or subject and may require medical or surgical intervention to prevent one of the endpoints listed in this definition.

AESIs and SAEs will be recorded from time of informed consent up to 30 days after trial medication discontinuation.

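### After open-label drug stops at Week 52, Protocol 10.3.11 asks for 14 days of AESI/SAE reports that Protocol 17.2.1 does not collect

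*Protocol*

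**What the plan says.** Two rules are written specifically for extension participants.

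- Protocol 17.2.1 sets the collection period: "For participants continuing in the Open-Label Extension Period, AESIs/SAEs will be collected up to and including the Week 52 visit".
- Protocol 10.3.11 ends treatment at that visit: "Stop study medication and prescribe alternate BP-lowering treatment in line with local guidelines/practice". It then tells sites: "Ask participants to report any AESIs/SAEs during 14 days after the end of study medication". Its last bullet has the site explain that follow-up is complete.

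The last column of Table 6 is Week 52, so no later contact is scheduled.

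Two general rules mention 30 days.

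- Protocol 17.2.3 requires SAEs that staff become aware of from consent "until 30 days after discontinuation of the trial medication must be recorded". It also says: "All SAEs will be reported by the site staff to the sponsor via the eCRF within 24-hours of first becoming aware of the event".
- SAP 3.11.1.1 says: "AESIs and SAEs will be recorded from time of informed consent up to 30 days after trial medication discontinuation". However, SAP 3.5.3 says: "Analysis of the optional Open-Label Extension Study will be described in a separate analysis plan".

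On reporting, Protocol 9.2.3 lists AESIs and SAEs "by trial medication group during the randomized treatment period, and safety follow-up period or Open-Label Extension Period". Protocol 9.3 makes the extension outcomes descriptive and non-comparative.

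**The concern.** A site that follows 10.3.11 asks the participant to report events for two weeks after the drug stops. A site that follows 17.2.1 has already closed collection. If the participant rings on day 5 with ankle swelling or dizziness, both of which are AESIs under Protocol 17.1.2, the protocol has asked for the report but gives no collection period in which to enter it. Sites can reasonably resolve this in different ways, and the extension safety data would then depend partly on local interpretation.

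Longer-term safety in the extension is a secondary objective (Protocol 6.2). Titration there can go beyond the randomized doses, up to GMRx2 dose 3 plus telmisartan 40 mg/amlodipine 5 mg plus spironolactone 25 mg (Protocol 8.4.3). The days just after the drug stops are therefore of some clinical interest.

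**Working it through.** No power or error-rate figure is involved. The check sets the windows side by side, counting days from a last open-label dose at the Week 52 visit.

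| Source | Written for the extension? | Non-serious AESIs | SAEs |
|---|---|---|---|
| Protocol 17.2.1 | Yes | 0 days | 0 days |
| Protocol 10.3.11 | Yes | 14 days | 14 days |
| Protocol 17.2.3 | Not stated | none given | 30 days, if staff become aware |
| SAP 3.11.1.1 | Doubtful | 30 days | 30 days |

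**Step 1: the firm conflict.** The first two rows are both extension-specific, and neither defers to the other. The gap is 14 − 0 = 14 days. This needs neither the SAP nor any reading of what counts as trial medication. The closing sentence of 17.2.1, on information after the end-of-trial visit, concerns events already ongoing, so it does not settle what happens to new ones.

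**Step 2: who is affected.** A participant who stopped open-label drug d days before the Week 52 visit, and stays under follow-up to that visit, already has d days covered. The shortfall against 10.3.11 is 14 − d days, or 0 once d is 14 or more. Only participants on drug within 14 days of Week 52 are exposed. The documents do not give their number.

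**Step 3: SAEs.** The 30-day rule in 17.2.3 carries no exemption for the extension, and Table 6 calls the open-label drug trial medication. On that reading an SAE on days 1 to 30 is still recorded once the site learns of it. Two passages point the other way. Protocol 7.1 ties the 30-day assessment to the safety follow-up period, which the extension replaces (Protocol 7, figure legend). Protocol 8.8 describes discontinuation of trial medication only before Week 4. Section 8.8 is about early discontinuation, though; applied throughout, it would also exclude ordinary Week 4 completers from 17.2.3. The reach of the rule is plausible but unstated.

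**Step 4: is 14 days a sensible window?** Protocol 5.6 gives amlodipine a half-life of 30 to 50 hours, and Appendix 5 uses 5 half-lives as a washout measure. 5 × 30 = 150 hours, or 6.25 days; 5 × 50 = 250 hours, or about 10.4 days. Fourteen days covers this residual exposure and 0 days does not.

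**Step 5: comparison with participants outside the extension.** From Table 5, the Week 8 call falls nominally 56 − 28 = 28 days after the Week 4 stop. With the ±7-day windows the range is (56 − 7) − (28 + 7) = 14 days to (56 + 7) − (28 − 7) = 42 days. They have one scheduled contact after stopping drug; participants stopping at Week 52 have none.

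**The case against.** The strongest reply is that this is a small wording mismatch that should not be inflated. Much of that stands.

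- **Four competing windows.** A reader might infer conflicting periods of 0, 14, 30 and 30 days. The documents do not support that. SAP 3.5.3 defers the extension to another plan. SAP 3.11.1.1 describes AESIs as arising in run-in, the randomized period and follow-up, and the summary periods in SAP 3.11.1.2 likewise omit the extension. SAP 2.4.2.2 does name the extension, but it repeats the protocol's outcome list. The SAP's 30 days cannot be relied on after Week 52.
- **Lost SAEs.** A reader might also infer that SAEs go unrecorded after Week 52. If 17.2.3 applies, they have a passive route. If it does not, there is no 30-day rule to conflict with, and SAEs share the 0 versus 14 day mismatch.
- **No outcome needs these data.** Protocol 9.2.3 covers events in the Open-Label Extension Period, and Protocol 8.4.3 makes Week 52 the end of that period. Events on days 1 to 14 arguably fall after it. This limits the consequence, but 10.3.11 itself asks for the reports, so the plan should say what becomes of them.
- **10.3.11 is only advice to participants.** Asking for reports that the collection rule excludes is the defect, whoever the sentence addresses.

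**Conclusion.** The point holds in a narrow form. For participants on open-label drug to Week 52, Protocol 17.2.1 collects AESIs and SAEs for 0 days off drug, while 10.3.11 asks for reports for 14. The firm loss is new non-serious AESIs on days 1 to 14, which are solicited but fall outside the collection period. For SAEs the text needs clarifying: the safeguard in 17.2.3 depends on its reaching open-label drug.

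The impact is minor. Only descriptive, non-comparative open-label safety data are affected, and no randomized Week 4 comparison changes. How many events are involved cannot be estimated, because the documents give neither the number on drug at Week 52 nor an event rate for those days.

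**What to change.** Amend Protocol 17.2.1 so that, for extension participants, new AESIs and SAEs are collected and entered in the eCRF until at least 14 days after the last open-label dose, matching 10.3.11. State in 17.2.3 that its 30-day SAE rule also applies after open-label drug stops. A uniform 30 days in both 17.2.1 and 10.3.11 is an acceptable alternative. If the extension has already closed, which the documents do not say, its separate analysis plan should state which window was applied.

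A closing telephone contact in Table 6 is optional. At about day 30 it could also serve the pregnancy reporting window in Protocol 17.2.5, but it would not detect laboratory AESIs.

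The cost is a few sentences of protocol wording and slightly more event entry. Participants will by then have been prescribed alternate BP-lowering treatment, so causality assessment of these events needs care. The optional call would add one column to Table 6 and one short call per participant still on drug near Week 52.

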11. METHODS: ASSIGNMENT OF INTERVENTION

11.1. Allocation Sequence Generation

A central, computer-based randomization sequence will be generated, stratified by trial site.

11.2. Allocation Concealment

Randomization sequence will be incorporated into an online electronic data capture (EDC) application by a statistician. Neither the Investigators nor site staff will have access to the randomization sequence. Participants meeting eligibility for randomization, can be randomized in the online EDC. The EDC application will generate the randomization record with the participant identification number and date and time.

11.3. Blinding (Masking)

Neither the site staff, including those measuring the outcomes nor the participants will be aware of the treatment allocated since all trial medication will be provided in identical capsules. Access to information on allocated treatment will be restricted. Breaking of treatment code (unblinding) will be restricted to situations that necessitate ascertainment of type of medication for a given participant to provide appropriate care. To protect blinding, all medications will have an identical appearance. None of the trial committees will have access to the code list of allocated treatments.

11.4. Unblinding

11.4.1. Unblinding of Trial Medication for Expedited Safety Reporting

Where country regulatory safety reporting requirements mandate the reporting of unblinded data, treatment assignment will be unblinded before they are reported to the Competent Authorities and IRB/IEC in accordance with the local safety reporting requirements. The trial medication assignment will only be made available to the relevant Competent Authorities and IRB/IEC and not be communicated to participants, investigators, or the CRO staff.

11.4.2. Unblinding of Trial Medication in a Clinical Emergency

In general, unblinding will only be required in certain specific circumstances which are expected to be very rare. If a contraindication to trial medication develops after randomization, the trial medication should simply be stopped and usual standard care given. Unblinding should be done only in those rare cases when the clinician believes that clinical management depends importantly upon knowledge of which treatment the participant received. In these cases when urgent unblinding is considered necessary, a 24-hour access service will be available. An unblinding report form should then be completed by the investigator.

12. METHODS: DATA COLLECTION, MANAGEMENT & STATISTICAL ANALYSIS

12.1. Data Collection

The investigator will be responsible for ensuring the accuracy, completeness, and timeliness of the data collected for the trial. All source data should be legible and complete to ensure accurate interpretation.

The trial will use an eCRF for data collection. Trial site staff will be trained on eCRF. Delegated site staff provided with the access (with username, password) will enter data in the eCRF regularly according to instructions for completion and any data queries will be resolved promptly. Data entered in eCRF should be consistent with the source data. For home BP values, the home BP machine is the data originator and the eCRF is regarded as the source record.⁶³ For BP values measured in clinic in which a paper transcription step is used, then the paper documentation should be retained and made available for inspection.⁶³ The investigator will sign each participant's eCRF confirming and certifying that the data entered is accurate and complete. All data collected in the eCRF will be securely stored with access restricted to representatives authorized for data management, and data analysis at the end of the trial.

12.2. Data Management

All data entry will be completed via the secure web-based data management system, IBM Clinical Development. Data entry will be performed at the participating sites by authorized site staff who have completed training and been given appropriate role-based access to the system. Data logic and consistency checks will be programmed into the data entry forms so that data entry errors can be caught real time and queries auto-generated. Manual queries may also be generated and listings will be run to perform manual data checks which cannot be programmed. Authorized electronic signatures will be used to lock completed data entry forms once all data queries have been resolved within the system. Data entry and all subsequent changes or deletions will be captured in an accessible audit trail. Coding will be centrally performed either automatically via the IBM coding module or manually. Data will be stored and backed up on the IBM's cloud servers in the USA.

12.3. Sample Size & Power Calculation

A total of 250 participants will be randomized, with a 2:2:1 ratio of triple $\frac{1}{4}$: triple $\frac{1}{2}$: placebo, which is likely to necessitate over 300 entering the placebo run-in treatment period. Assuming a common standard deviation of 11 mmHg, this sample size will provide >90% power to detect differences in mean home SBP of 9 mmHg and 13 mmHg respectively for the comparisons of triple $\frac{1}{4}$ vs placebo and triple $\frac{1}{2}$ vs placebo, respectively. For the comparison of triple $\frac{1}{4}$ vs triple $\frac{1}{2}$ there will be >80% power to detect a difference of at least 4.5 mmHg in mean home SBP.

12.4. Statistical Methods

All analyses will be performed on an intention-to-treat basis. Baseline characteristics by the group will be compared using descriptive analyses. The primary outcome of difference in change in home SBP from baseline to Week 4 will be analyzed using a mixed model with baseline BP and treatment group as fixed effect and accounting for clustering at the site level. Other continuous outcomes of difference in change in BP will

also be analyzed as the primary outcome. All continuous outcomes will be reported along with 95% CI and the corresponding p-value. The percentage of participants achieving target BP at Week 4 will be summarized descriptively and analyzed using a generalized estimating equation to account for clustering at the site level. Percentages by treatment groups with 95% CI will be presented along with the associated estimated RR and its corresponding p-value. Other binary outcomes of efficacy and safety will be analyzed as the percentage of participants achieving target BP. The primary analysis dataset will be locked after the last participant has reached the 8-week follow-up visit.

13. WITHDRAWAL FROM TRIAL PARTICIPATION

Participants will be informed at the time of consenting and enrolment that; they are free to withdraw from the trial at any time and for any reason without influencing any aspect of their usual medical care. If a participant wishes to withdraw from the study prior to completion and explicitly revokes consent or if the trial investigator decides it is in the best interest of the participant to withdraw from the trial, every effort should be made for the participant to complete a final follow-up assessment to record BP, AESI and SAEs and collect all unused trial medication. Data collected up to the point of withdrawal will be included in trial analyses unless the participant expressly requests their data to be excluded.

14. TRIAL MEDICATION MANAGEMENT

14.1. Manufacturing

The formulation development and manufacturing of GMRx2 will be conducted as per Good Manufacturing Practice and in accordance with the applicable regulatory requirements.

14.2. Packaging, Labelling, Distribution & Storage

Packaging, labeling, quality release, storage, and distribution of the trial medication to the local country depot or directly to participating sites will be conducted as per the local regulatory and set-up requirements. All shipments will be temperature-monitored, and where required, temperature-controlled shipments will be conducted. The CRO will keep accurate records of trial medication supplies to trial sites. At each trial site, the Investigator will be responsible to store and maintain accurate records of trial medication and report to the CRO. Trial sites will store trial medication as per the labeled instructions and will instruct the trial participants accordingly.

14.3. Return & Destruction

At the end of the trial, following the accountability of the returned/unused trial medication, and on the authorization of the ACC, trial medication will be destroyed on-site or returned to the depot for destruction. Once destroyed, a destruction certificate or record will be provided to the site.

15. MANAGING INTERRUPTION OF STUDY MATERIAL SUPPLY TO TRIAL CENTRES

Supply chain-related interruptions of study materials to trial centres may occur, especially in the context of a pandemic, in which case the following strategies should be adopted. If study BP machines are not available at the centre, participants should not be entered into run-in, but asked to return when BP machines are available, which may necessitate re-screening. If study treatment for any trial phase (Period 1 (Run-in) or Period 2 as in Figure 3) is not available at the centre, the participant should delay the start of Run-in, which may necessitate rescreening. If a participant is on Run-in but Period 2 study treatment is not available, then randomization should be delayed, which may necessitate extending or repeating run-in.

16. MONITORING

16.1. Data & Safety Monitoring Board

An independent DSMB will monitor the trial data and advise the SC on the continuing safety of trial participants and those yet to be recruited to the trial, as well as the continuing validity and scientific merit of the trial.

16.2. Data Monitoring

In addition to pre-programmed edit checks in the eCRF, regular remote data monitoring will be conducted by the responsible CRO and designated monitors for confirmation of participant eligibility, identification of missing data, data consistency, and general data quality checks. Automated queries may be generated via programming in the eCRF and can also be manually generated by monitoring staff. On-site monitoring visits will also be conducted to review source documents and to resolve any issues at the site. Full details of monitoring activities will be described in the Trial Monitoring Plan. The investigator should allow the monitors, the persons responsible for the audit, the representatives of the sponsor, the IRB/IEC, and of the Regulatory Authorities to have direct access to source data/documents. The CRO will also undertake regular remote monitoring of data.

